10.2.2. Efficacy Analyses

10.2.2.1. Primary Estimand

The primary estimand quantifies the treatment effect of MM-120 at 4 weeks post-dose administration while accounting for intercurrent events (IEs) with potential confounding effects and IEs leading to study discontinuation prior to the 4-week assessment.

The following attributes describe the primary estimand:

- Population: As defined by the Inclusion/Exclusion criteria
- Endpoint: Change from Baseline to Week 4 in HAM-A Total Score
- Treatment of interest /the randomized treatment: 4 doses of MM-120 (25, 50, 100, or 200 µg free-base equivalent) or placebo as a single-dose treatment.
- Handling of IEs prior to HAM-A assessment at Week 4:
 - Intake or change in concomitant medications/therapies which have potential confounding effects per the impact assessment.
 - Intake of prohibited medications/therapies assessed as "Yes" per the impact assessment.
 - *Policy strategy:* Available data recorded after the IE will be set to missing; such missing data will be imputed/substituted under a Missing Not at Random (MNAR) assumption by borrowing information from the placebo arm subjects (reference-based imputation).
 - IEs leading to study discontinuation due to other reasons.
 - IEs related to the COVID-19 pandemic
 Policy strategy: Available data will be used; missing data will be imputed under a Missing at Random (MAR) assumption, borrowing information from subjects in the same treatment arm.
- Summary measure: Identification of the dose-response curve and estimation of the target dose

Statistical Methods & Analysis

The MCP-Mod methodology (Bretz 2005; Pinheiro 2014) will be employed to assess the primary objective: to investigate the dose-response relationship for different doses of MM-120 versus placebo in change from Baseline in HAM-A Total Score at Week 4. An overview of the steps for the MCP-Mod methodology is given below.

Step 1

The analysis to derive the test statistics is based on an analysis of covariance (ANCOVA) model with the change from Baseline to Week 4 for HAM-A Total Score as a response variable, treatment (placebo and all MM-120 doses), and Baseline value of HAM-A Total Score. Centers will be pooled according to country and region as appropriate and as defined in the SAP prior to unblinding.

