## 4.2 Analysis Sets

The following populations will be defined for the purpose of analysis:

- Randomized Set (RAN) all subjects who received a randomization number, regardless of receiving study drug. Subjects will be analyzed according to the treatment assigned.
- Safety Set (SAF) all subjects who received the double-blind study drug. Subjects will be analyzed according to the actual treatment received.
- Full Analysis Set (FAS) all randomized subjects with a valid baseline HAM-A assessment and at least one valid post-baseline HAM-A assessment. Subjects will be analyzed according to the treatment assigned.
- Per Protocol Set (PPS) All subjects in the full analysis set who had no major protocol deviations deemed as impacting the primary endpoint. Subjects will be analyzed according to the actual treatment received.

An impact assessment will be performed prior to the unblinding of the study. The impact assessment will determine whether a major protocol deviation impacts the primary endpoint thereby leading to the removal of the respective subject(s) from the PPS.

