## 6.1.1 Handling of Missing Data and Potentially Biased Values

Missing data for the primary endpoint will be imputed using a multiple imputation approach assuming that the missingness mechanism can be retrieved from observed data. The imputation model will include the treatment group and the longitudinal sequence of HAM-A Total Score. Imputations will be performed 20 times using SAS PROC MI with the fully conditional specification (FCS) method.

For intercurrent events (IEs) the following methods will be used:

- The data recorded after the IE will be set to missing and imputed under a Missing Not at Random (MNAR) assumption by borrowing information from the placebo arm subjects (reference-based imputation) for the following:
  - Concomitant/prohibited medications that meet the threshold for impact = "Yes" during the impact assessment will be considered as the IE. Any observations after such an IE will be set to missing and will be imputed using the MNAR assumption.
- Available data will be used; missing data will be imputed under a Missing at Random (MAR) assumption, borrowing information from subjects in the same treatment arm for the following:
  - For IEs leading to study discontinuation due to other reasons
  - IEs related to the COVID-19 pandemic.

For missing data not due to IEs the imputation will be performed based on MAR assumption.

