## 6.2 Key Secondary Efficacy Endpoint and Analysis

## 6.2.1 Key Secondary Endpoint

The key secondary endpoint is change from Baseline to Week 8 in HAM-A Total Score. Analysis of this endpoint will follow the same process as the primary endpoint described in Section 6.1. The outcome for this endpoint will be considered confirmatory, if in agreement with the primary endpoint outcome and provided that the null hypothesis is rejected for the primary outcome. This gatekeeping function of the primary outcome allows for no adjustment of alpha level for multiplicity of testing.

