## 8 INTERIM ANALYSIS AND CHANGES FROM PROTOCOL

No formal interim analysis was planned for the study.

During the conduct of the study, a Sponsor decision was made to perform the analysis of the primary endpoint when all enrolled subjects reached their Week 4 visit. The approximately 180 subjects will provide adequate power to determine the dose-response relationship as defined in the primary objective of the study. No further subjects will be enrolled, and the study will continue to its normal conclusion.

This 'Top-Line' analysis will be the final analysis for the HAM-A primary endpoint at Week 4, HAM-A response and remission through Week 4, HAM-A change from baseline through Week 4, MADRS change from baseline through Week 4 and CGI-S through Week 4. Preliminary analysis of Subject Disposition, and Adverse Events will be provided as well. As this will be the final analysis for the select efficacy endpoints through Week 4, this is not considered an interim analysis and no adjustment to the overall alpha level of the trial is needed.

At the time of analysis, data for the select efficacy analyses through Week 4 will be cleaned and locked in the clinical trial database according to the Data Management Plan. Supporting data for the preliminary analyses will be cleaned and frozen, and a snapshot of the database taken.

A pre-defined unblinded statistician and programmer, not involved with the conduct of the study, will perform this analysis. The Study team will remain blinded through the completion of the study. The topline results for the primary endpoint will not be available to the Study Team or externally until the final subject has completed their last visit assessment.

The remaining secondary efficacy analyses and final safety analyses will be conducted at the completion of the trial.

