## 9 SAMPLE SIZE AND POWER CALCULATIONS

A total sample of 180 subjects, 36 per arm, is required to ensure a mean power >87% for an MCP-Mod Analysis rejecting the hypothesis of a constant dose-response curve using the multiple comparisons procedure (MCP), assuming a null placebo response, a maximum standardized effect of 0.6 within the doses range, and a common standard deviation within the dose arms, if a studywise one-sided type-1 error rate <0.05 is required.

The analysis assumes 4 doses of active medication (25, 50, 100 and 200  $\mu$ g freebase-equivalent) and placebo. The required sample size for each arm is 36 subjects.

The R package Dose Finding (https://CRAN.R-project.org/package=DoseFinding) has been used to estimate the sample size and corresponding power. The power for each model is estimated as shown Table 6.

Table 6	Power by Mode

Model	Power (%)
Sigmoid Emax (ED50, hill)	
10, 1	84.5
100, 5	90.7
100, 10	91.0
150, 10	89.9
Emax (D50 = 100)	83.2
Linear	85.0

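### The impact assessment is tied to the Week 4 endpoint, so the per-protocol set used at Week 8 ignores medication switches made after Week 4, and their intercurrent-event handling at Week 8 is ambiguous

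*SAP*

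**What the plan says.** SAP 4.2 describes one impact assessment, made before the study is unblinded. Its purpose is to "determine whether a major protocol deviation impacts the primary endpoint", and the stated consequence is removal from the PPS. The footnote to Protocol Table 8 agrees. SAP 6.1 defines the primary endpoint as the HAM-A change to Week 4.

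The same assessment identifies intercurrent events. SAP 6.1.1 counts as the event "Concomitant/prohibited medications that meet the threshold for impact", meaning a rating of Yes. Later scores are set to missing and imputed from the placebo arm. It does not define the threshold and names no week. Protocol 10.2.2.1 introduces its list with "Handling of IEs prior to HAM-A assessment at Week 4". That section also mentions medications with potentially confounding effects, again as judged by the impact assessment.

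For the key secondary endpoint, SAP 6.2.1 says: "Analysis of this endpoint will follow the same process as the primary endpoint described in Section 6.1". It gives no Week 8 estimand, impact criterion or PPS. Week 8 is the second test in the fixed sequence (SAP 4.6), and Protocol 2.2.2 names it as the measure of durability. Protocol 6.10.1 prohibits treatments for anxiety, depression or mood disorders from Baseline to End of Study, apart from a dosing-day exception.

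SAP 8 adds that the sponsor decided to "perform the analysis of the primary endpoint when all enrolled subjects reached their Week 4 visit", while the study team stays blinded to the end.

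**The concern.** A drug started after the Week 4 HAM-A cannot change that score. Under the only criterion the plan states, such a drug has no impact, even though it breaches the protocol and may lower the Week 8 HAM-A. Two consequences follow at Week 8:

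- **PPS.** The subject stays in the set, so the PPS sensitivity analysis cannot show whether the Week 8 result depends on these switches.
- **Intercurrent-event flag.** If the flag takes its criterion from SAP 4.2, the drug is not an intercurrent event and the post-switch score counts as an outcome of the randomised arm.

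The test at stake is the only secondary test with type I error protection. If placebo or low-dose subjects switch more, kept scores flatten the dose-response. If active-arm subjects switch more, kept scores overstate durability. The Week 4 primary analysis is not affected.

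**Working it through.** **1. The plan's own power figure.** The inputs, from SAP 9 and 3.2.1, are "A total sample of 180 subjects, 36 per arm, is required to ensure a mean power >87"%, "if a studywise one-sided type-1 error rate <0.05 is required", "a maximum standardized effect of 0.6 within the doses range", a common SD (set to 1) and equal allocation. The doses are 0, 25, 50, 100 and 200 µg, with the six candidate curves of SAP 6.1.2.

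- Arm means for curve f: μ(d) = 0.6 × [f(d) − f(0)] / [f(200) − f(0)].
- Contrast c: μ minus its average, scaled to length 1.
- Noncentrality: √36 × c′μ. Degrees of freedom: 180 − 5 = 175.
- The simulated multivariate-t critical value (400,000 draws) is 2.045.

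Power is 84.5, 90.7, 91.0, 89.9, 83.2 and 85.0%, with mean 524.3 / 6 = 87.4%. All six values match SAP Table 6. This figure does not depend on the intercurrent-event rule. It only provides a checked base for step 3.

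**2. One subject followed through the rules.** The Week 4 HAM-A is on Day 29, a prohibited anxiolytic starts on Day 35, and the Week 8 HAM-A is on Day 57.

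| Question | Source | Result |
|---|---|---|
| Is it a breach? | Protocol 6.10.1 | Yes, the prohibition runs to End of Study |
| Does it impact the primary endpoint? | SAP 4.2, 6.1 | No, the Day 29 score came first |
| Removed from the PPS? | SAP 4.2, Protocol Table 8 | No |
| PPS used at Week 8? | SAP 6.2.1 through 6.1; also 6.3.1 | Yes |
| Flagged, using the SAP 4.2 criterion? | SAP 6.1.1 with 4.2 | No, Day 57 score used |
| Flagged, reading Week 8 for Week 4 in SAP 6.1.1? | SAP 6.1.1 with 6.2.1 | Yes, Day 57 score set to missing |

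The PPS answer is the same on either reading; the flag answer is not. Discontinuation does not close the gap. Protocol 7.2 says a subject needing an excluded drug may be discontinued, and asks for an Early Withdrawal visit with the Week 12 assessments, which include the HAM-A. SAP Table 1 assigns a HAM-A on Days 44 to 71 to Week 8.

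**3. Illustration of size (assumed inputs).** Let p0 and pa be the proportions switching between Weeks 4 and 8 on placebo and at 200 µg, and e the gain from switching in SD. The true Week 8 effect is taken as 0.6. For 200 µg against placebo:

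- scores kept: 0.6 − (p0 − pa) × e
- set to missing with placebo-based imputation: 0.6 × (1 − pa)

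The value e = 0.39 is the overall effect size for drugs in generalised anxiety disorder cited in Protocol 2.1.1; e = 0.6 is an assumed upper case. Power is the mean over the six curves. Ranges cover two patterns: the same switch rate at every active dose, or a rate falling from p0 to pa as response rises.

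| p0 | pa | e | Difference, kept | Difference, imputed | Power, kept | Power, imputed |
|---|---|---|---|---|---|---|
| 5% | 5% | 0.39 | 0.60 | 0.57 | 0.873–0.874 | 0.842 |
| 20% | 10% | 0.39 | 0.56 | 0.54 | 0.831–0.845 | 0.803–0.804 |
| 20% | 5% | 0.39 | 0.54 | 0.57 | 0.806–0.832 | 0.840–0.842 |
| 30% | 10% | 0.39 | 0.52 | 0.54 | 0.780–0.818 | 0.803–0.805 |
| 30% | 10% | 0.60 | 0.48 | 0.54 | 0.715–0.783 | 0.803–0.805 |

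If active subjects switch more (p0 = 5%, pa = 10%, e = 0.39), keeping scores gives 0.6 + 0.05 × 0.39 = 0.62, against 0.6 × 0.90 = 0.54. Switching is modelled as a shift in means only, with no allowance for imputation uncertainty.

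**The case against.** The strongest reply is that SAP 6.2.1 means what any analyst would take it to mean: read Week 8 for Week 4 throughout. The Week 4 limit in Protocol 10.2.2.1 stands under the primary estimand, where Week 4 is naturally named. SAP 6.1.1 has no week limit, and the protocol also speaks of potentially confounding effects, which a drug started on Day 35 plainly could have at Day 57. The sentence in SAP 4.2 concerns the PPS and does not itself define the flag.

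Much of this stands. A reader might infer that the plan keeps post-switch scores at Week 8. No passage says so, and the substitution reading is open. But the substitution works inside Section 6.1. It does not alter Section 4.2, where the criterion and the PPS are defined. The confounding-effects wording also refers back to the impact assessment, for which no Week 8 test is stated.

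A reader might also infer that the assessment must be finished before the Week 4 top-line analysis and so cannot cover later medications. The documents do not support that. It must precede study unblinding, only a designated statistician and programmer are unblinded for the top-line work, and SAP 3.2.2 places database unblinding at the end. A later blinded rating is possible; it is just not written down.

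Two limits also apply. The example needs a Week 4 HAM-A taken before the drug was started. The Week 4 window runs to Day 43, so a late assessment could itself follow the switch and be affected. And nothing in the documents shows that switching is most likely after Week 4.

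**Conclusion.** The point holds in a limited form. The PPS rule is clear and unsuited to Week 8: a prohibited drug started between the Week 4 and Week 8 HAM-A does not exclude the subject. The intercurrent-event rule at Week 8 is ambiguous: on one literal reading the post-switch score enters the key secondary analysis, on another it is set to missing.

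The size and direction of the effect are unknown because the documents give no switching rates. Under the assumed rates of 5–30% on placebo and 5–10% on active drug, with a gain of 0.39–0.6 SD, mean Week 8 power is 0.72–0.87 with scores kept and 0.80–0.84 with imputation. Neither handling is uniformly more favourable. These figures are illustrative; they show only that the choice can matter and should be settled before the treatment codes are known.

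**What to change.** In SAP 4.2, 6.1.1 and 6.2.1, make the impact assessment endpoint-specific:

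- Rate each medication or therapy deviation for the Week 4 HAM-A and, separately, for the Week 8 HAM-A.
- Have the still-blinded study team complete the Week 8 rating before final lock and unblinding. The SAP addendum records that analyses were added after an unblinded review of the primary endpoint, so document that the raters had not seen treatment codes.
- For Week 8, apply the plan's existing rule (set to missing, placebo-based imputation) to events rated Yes that occur before the Week 8 HAM-A.
- Define a Week 8 PPS from the Week 8 rating.

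A sensitivity analysis that keeps the post-switch scores would show how far the Week 8 result depends on the choice.

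The cost is some SAP wording, one extra column in the blinded review, a second short review, and slightly more imputed values at Week 8. No new data are needed.

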#### 4.3 Assessment Windows

Day 1 of the study will be defined as the date of first administration of study drug. Study Day will be measured relative to Day 1. Select efficacy endpoints will use analysis visit windows for the assigning of efficacy data to visits. Data from all scheduled and unscheduled visits will be included in these analyses. All other endpoints will be summarized/analyzed using the nominal study visit. Analysis visit windows are defined for the select efficacy endpoints in the tables below. The data point within an analysis visit window that is closest to the target visit day will be assigned to the respective analysis visit. In case of ties, the data point associated with the largest study day (i.e.; the latest data point) will be assigned to the respective analysis visit.

Analysis Visit	Target Study Day	Analysis Visit Window
Baseline	1-5 days prior to Day 1	<= Day 1
Week 1	Day 8	>= Day 2 and <= Day 11
Week 2	Day 15	>= Day 12 and <= Day 21
Week 4	Day 29	>= Day 22 and <= Day 43
Week 8	Day 57	>= Day 44 and <= Day 71
Week 12	Day 85	>= Day 72

Table 1 Analysis Visit Windows for HAM-A, MADRS, SDS, EQ-5D-5L, and ASEX

Analysis Visit	Target Study Day	Analysis Visit Window
Baseline	1-5 days prior to Day 1	<= Day 1
Day 2	Day 2	>= Day 2 and <= Day 4
Week 1	Day 8	>= Day 5 and <= Day 11
Week 2	Day 15	>= Day 12 and <= Day 21
Week 4	Day 29	>= Day 22 and <= Day 43
Week 8	Day 57	>= Day 44 and <= Day 71
Week 12	Day 85	>= Day 72

Table 2 Analysis	Visit Windows	for CGI-S and PGI-S
------------------	---------------	---------------------

#### Table 3 Analysis Visit Windows for CGI-I and PGI-C

Analysis Visit	Target Study Day	Analysis Visit Window
Day 2	Day 2	>= Day 2 and $<=$ Day 4
Week 1	Day 8	>= Day 5 and <= Day 11
Week 2	Day 15	>= Day 12 and <= Day 21
Week 4	Day 29	>= Day 22 and <= Day 43
Week 8	Day 57	>= Day 44 and <= Day 71
Week 12	Day 85	>= Day 72

#### Table 4 Analysis Visit Windows for PSQI

Analysis Visit	Target Study Day	Analysis Visit Window
Baseline	1-5 days prior to Day 1	<= Day 1
Week 4	Day 29	>= Day 2 and <= Day 43
Week 8	Day 57	>= Day 44 and <= Day 71
Week 12	Day 85	>= Day 72

## 4.4 Unscheduled Visits

Unscheduled visits will be included in select efficacy analyses as noted above and will be presented in relevant subject listings. In certain circumstances laboratory test results from local labs, noted as 'unscheduled' will replace missing values from the central laboratory tests. In situations where a laboratory blood draw was performed according to the protocol schedule, but the central laboratory was unable to produce test results, another blood draw was performed, noted as 'unscheduled', and sent to the local laboratory. These local laboratory results will be reclassified as the visit in question and will be used for analysis.

## 4.5 Handling of Dropouts or Missing Data

Missing data on demographics, baseline information and safety measures will be treated as missing; no imputation is planned.

Missing or partial dates and times will be imputed for analysis purposes in a manner that imputes the most conservative date or time. Imputation methods for dates and times are described for each endpoint where applicable.

Details of missing data imputation will be specified in the analysis methods for the primary and key secondary efficacy endpoints. Subject-completed questionnaires will be considered missing if incomplete. Missing data will not be imputed for analysis of non-key secondary efficacy endpoints or safety endpoints.

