10.2.2.4. Secondary Efficacy Endpoints

Change from Baseline to Week 1, Week 2 (as applicable), Week 4, Week 8 and End of Study (as applicable) in HAM-A, MADRS, CGI-S, CGI-I, PGI-S, PGI-C, SDS, EQ-5D-5L, PSQI and ASEX will be analyzed descriptively. Continuous outcomes will be summarized by: n, mean, standard deviation, median, Q1 (25th percentile), Q3 (75th percentile), minimum, maximum and 95% Confidence Interval for the mean. For the active doses similar statistics will be reported for the difference from placebo. Categorical measures will be summarized by the number and percentage of subjects within each category.

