## Step 1

A test statistic will be derived from the data using an analysis of covariance (ANCOVA) model with change from Baseline to Week 4 for the HAM-A Total Score as a response variable, treatment arm and Baseline value of HAM-A Total Score as covariates. Geographic region will be included as a covariate if clinical sites outside the US are used; otherwise, it will not be included in the model. Missing or potentially biased values occurring after IEs will be imputed as described in Section 6.1.1.

The ANCOVA model will be repeated for each imputed dataset, which results in a set of least squares (LS) mean estimates for all dose groups and the related covariance matrices. Rubin's rule will be used to combine the multiple sets of LS mean estimates and the related covariance matrices to a single set of LS mean estimates of change from Baseline to Week 4 for HAM-A Total Score for all dose groups and the related covariance matrix. The SAS procedure PROC MIANALYZE will be used to combine the results from imputed datasets and provide valid statistical inferences.

A range of possible dose-response relationships will be considered to take model uncertainty into account. The following six candidate dose-response curves, as depicted below in Figure 1, will be used to derive the optimal model contrasts for the multiple contrast tests:

- Sigmoid Emax (ED50, hill):
  - o 10, 1
  - o 100, 5
  - o 100, 10
  - o 150, 10
- Emax (D50 = 100)
- Linear

The optimal contrasts derived from the candidate model sets will be applied to the combined estimated dose means and covariance matrix to obtain the t-statistics for each candidate model and the common critical value  $C_{0.05}$  derived from the reference multivariate t-distribution with the 6x6 correlation matrix induced by testing the candidate dose-range models with respect to comparing all MM-120 doses to the placebo group.

The null hypothesis will be rejected and the statistical significance of dose-response in change from Baseline to Week 4 for HAM-A Total Score will be established if the max ( $t_1$ ,  $t_2$ ,  $t_3$ ,  $t_4$ ,  $t_5$ ,  $t_6$ )  $\ge C_{0.05}$ .

Mind Medicine, Inc. MMED008 Statistical Analysis Plan (Final version 1.0)

## Step 2

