The response data in each imputed data set, including relevant covariates, will be used to fit the models in the candidate set. The estimated dose-response will be derived by using model averaging methods on a subset of candidate models, for which the associated contrast tests are statistically significant. The  $\leq$  3 models with the largest t-statistics  $\geq$  C0.05 as calculated above will be selected as the basis for the model averaging.

Dose

Model averaging will be carried out for each imputed dataset, and the resulting mean efficacy estimates, and CIs will be derived using the combination variance that accounts for the uncertainty of the imputed data using Rubin's combination rules. Comparisons between MM-120 doses and placebo will be simultaneously derived for the model averaged estimates together with the CIs reflecting the imputation procedure applied. The model-averaging-based estimates of the mean changes from Baseline to Week 4 for HAM-A Total Score within each dose group, and the mean

differences between MM-120 and placebo and their CIs will then be displayed.

Target dose selection (e.g., minimum effective dose [MED], EDp) will be based on the model change from Baseline to Week 4 for the HAM-A Total Score over the dose range studied. MED is defined as the lowest dose ensuring a clinically relevant and statistically significant improvement, MED = min{ $d \in (d_1, d_5) : f(d) > f(d_1) + \Delta$ }, where  $\Delta$  is the clinical relevance threshold. EDp is defined as the lowest dose that gives a certain percentage p of maximum effect  $\delta_{max}$ . EDp = min{ $d \in (d_1, d_5) : f(d) > f(d_1) + p\delta_{max}$ }. For this analysis, p will be set to 100%. The final choice of the target dose depends on the evaluation of the primary efficacy variable and other efficacy variables, as well as safety considerations.

The above will be repeated using only the model with the largest t-statistic  $\geq C_{0.05}$ .

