## 6.3.1 Change from Baseline in HAM-A Total Score

In addition to the primary and key secondary analysis for HAM-A, descriptive statistics will be presented for actual values and change from Baseline for scheduled visits. The change from Baseline will be analyzed using an analysis of covariance (ANCOVA) model including change from Baseline HAM-A Total Score as dependent variable, the baseline HAM-A Total Score as a covariate and treatment group as a fixed effect. The Least Square Means (LS Means) for each treatment group compared to placebo will be reported along with associated 95% CI and p-value. The ANCOVA comparisons will be performed for Week 1, Week 2, Week 4, Week 8 and the End of Study visit and will be presented for both the FAS and PPS populations.

A by-subject listing of results by visit, including any unscheduled visits, will be provided.

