## **3** EFFICACY ANALYSIS

## 3.1 Change from Baseline in HAM-A Subscales – Somatic Anxiety and Psychic Anxiety

Two subscales will be defined from the HAM-A questionnaire.

Somatic Anxiety is defined as the sum of items 7 - 13 of the HAM-A questionnaire.

Psychic Anxiety is defined as the sum of items 1 - 6, and item 14 of the HAM-A questionnaire.

Descriptive statistics will be presented for actual values and change from Baseline for scheduled visits for the FAS and PPS analysis populations. The change from Baseline will be analyzed using an analysis of covariance (ANCOVA) model including change from Baseline HAM-A Somatic Anxiety, or Psychic Anxiety, score as dependent variable, the baseline HAM-A Somatic Anxiety, or Psychic Anxiety, score as a covariate and treatment group as a fixed effect. The Least Square Means (LS Means) for each treatment group compared to placebo will be reported along with associated 95% CI and p-value. The ANCOVA comparisons will be performed for Week 1, Week 2, Week 4, Week 8 and the End of Study visit and will be presented for both the FAS and PPS populations.

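### The per-dose HAM-A p-values in SAP 6.3.1 have no stated missing-data or intercurrent-event rule and, at Weeks 4 and 8, appear to be observed-case, unlike the primary and key secondary analyses

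*SAP*

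**What the plan says.** SAP 6.3.1 plans an ANCOVA of HAM-A Total Score change, with baseline score and treatment group in the model, at Weeks 1, 2, 4, 8 and End of Study, in both FAS and PPS: "The Least Square Means (LS Means) for each treatment group compared to placebo will be reported along with associated 95% CI and p-value". It mentions no imputed data sets, no Rubin combination and no handling of scores after an intercurrent event.

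The general rule in SAP 4.5 leaves imputation to the methods for the primary and key secondary endpoints, and then says: "Missing data will not be imputed for analysis of non-key secondary efficacy endpoints or safety endpoints".

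The primary analysis (SAP 6.1.1 and 6.1.2) works differently. Missing scores are multiply imputed 20 times. After a concomitant or prohibited medication judged to have impact, "Any observations after such an IE will be set to missing and will be imputed using the MNAR assumption", with information borrowed from placebo. In Step 1, "The ANCOVA model will be repeated for each imputed dataset" and the results are pooled by Rubin's rules. For Week 8, SAP 6.2.1 says "Analysis of this endpoint will follow the same process as the primary endpoint described in Section 6.1". The per-dose output of Step 2 is model-averaged: "differences between MM-120 and placebo and their CIs will then be displayed". No p-value is attached to it.

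Protocol 10.2.2.4 includes "Week 4, Week 8 and End of Study (as applicable) in HAM-A" in its list of secondary analyses. Addendum 3.1 reuses the 6.3.1 approach for the HAM-A subscales at the same visits, with a "model including change from Baseline HAM-A Somatic Anxiety, or Psychic Anxiety, score as dependent variable". Its only missing-data rule (Addendum 2.4) is the no-imputation sentence again.

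**The concern.** At Week 4 the plan produces two sets of dose results from the same population and the same ANCOVA covariates. One set, from Step 1, imputes missing scores and replaces post-event scores from placebo. The other, from 6.3.1, apparently does neither, and nothing in the SAP says that they differ.

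The 6.3.1 set will be read closely. It holds the only per-dose p-values for HAM-A Total Score, and SAP Section 8 makes the HAM-A results through Week 4 final in the top-line analysis. An observed-case difference is biased, in either direction, if score-related dropout differs between arms. Such dropout is possible under the protocol's own rules, since Protocol 7.2 allows withdrawal of a subject who comes to need an excluded medication.

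The treatment of post-event scores is a separate matter. Keeping or replacing them changes the estimand; it is not a bias. But a reader needs to know which one the p-value refers to.

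**Working it through.** **1. Is 6.3.1 the only source of per-dose p-values?** Step 1 gives a t-statistic per candidate model. Step 2 gives differences with CIs. Response and remission (6.4.1) and subgroups (6.5) have CIs only. The addendum's p-values are for subscales. So yes.

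**2. Which missing-data rule applies?** The section is placed under the secondary endpoints (6.3), is introduced as additional to the primary and key secondary analyses, and refers to no imputed data. Protocol 10.2.2.4 and the addendum fit that reading. On the other reading, Weeks 4 and 8 remain the primary and key secondary endpoints (SAP 2.2.1, 2.2.2) and carry imputation with them. One table would then mix imputed visits (4 and 8) with observed-case visits (1, 2, End of Study).

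**3. The plan's own figure.** It states none for these comparisons. Its MCP power table does reproduce. With optimal contrasts c, noncentrality = sqrt(36) x c'mu, maximum effect 0.6 SD, 175 df and a one-sided 0.05 critical value of 2.04, the powers are 84.6, 90.7, 91.0, 89.9, 83.2 and 85.1%. The stated values are 84.5, 90.7, 91.0, 89.9, 83.2 and 85.0%. This point does not touch that table.

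**4. Size of the bias (all inputs assumed).** True difference -5; SD of change 8 (0.625 SD, close to the plan's 0.6); Week 2-Week 4 correlation r of 0.5 or 0.7; baseline normal (28, SD 6) truncated at 20; dropout logistic with slope 1 per SD, worse scorers leaving. Simulation used 400,000 subjects per arm. Repeat runs agreed within about 0.05 points. Rates are the share with no Week 4 score, placebo/active.

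Dropout driven by the Week 2 score:

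| Rates | Observed-case, r=0.5 / 0.7 | Departure from -5 |
|---|---|---|
| 15%/15% | -5.03 / -5.01 | none |
| 10%/5% | -4.85 / -4.75 | 0.15 / 0.25 too weak |
| 20%/8% | -4.61 / -4.45 | 0.39 / 0.55 too weak |
| 30%/10% | -4.33 / -4.10 | 0.67 / 0.90 too weak |
| 5%/10% | -5.17 / -5.26 | 0.17 / 0.26 too strong |
| 10%/30% | -5.65 / -5.88 | 0.65 / 0.88 too strong |

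Within-arm imputation on baseline and Week 2 gives about -5.0 throughout, by construction. Against the standard error, the bias is 0.15/1.95 to 0.25/1.95, about 0.1 SE, at 10%/5%. At 30%/10% it is 0.67/2.1 to 0.90/2.1, or 0.3 to 0.4 SE.

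Dropout driven by the unseen Week 4 score:

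| Rates | Observed-case, r=0.5 / 0.7 | Imputed, r=0.5 / 0.7 | Share of bias removed |
|---|---|---|---|
| 10%/5% | -4.65 / -4.64 | -4.73 / -4.80 | 0.08/0.35 = 23%; 0.16/0.36 = 44% |
| 20%/8% | -4.20 / -4.19 | -4.38 / -4.55 | 0.18/0.80 = 23%; 0.36/0.81 = 44% |
| 30%/10% | -3.69 / -3.66 | -3.97 / -4.25 | 0.28/1.31 = 21%; 0.59/1.34 = 44% |

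When dropout is unrelated to scores, both methods give -5.0.

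**5. Effect on p-values.** 4,000 simulated two-arm trials per scenario, 36 per arm, Week 2-driven dropout, 20 imputations pooled by Rubin's rules, two-sided 0.05:

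| Rates | Chance of p<0.05, observed-case vs imputed | p-values on opposite sides of 0.05 |
|---|---|---|
| 10%/5% | 67-68% vs 70-71% | 6-8% of trials |
| 30%/10% | 49-52% vs 64-67% | 13-19% |
| 10%/30% | 75-79% vs 64-67% | not tabulated |
| 15%/15% | not tabulated | 7-10%, with no bias |

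With no true effect, the observed-case error rate is 5-7%.

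**6. Post-event scores (assumed rates).** If a fraction qa of the active arm and qp of placebo have an impacting medication, placebo-based replacement targets 0.6 x (1 - qa) SD: 0.57 at 5%, 0.54 at 10%, 0.48 at 20%. Keeping the scores targets 0.6 + b x (qa - qp), where b is the benefit of the added medication and the drug effect persists. With qp=30%, qa=10% and b=0.6 this is 0.6 - 0.12 = 0.48, against 0.54. With b=0 it is 0.60, against 0.54. The gap can go either way.

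**The case against.** The observed-case reading is not explicit. SAP 4.5 and 6.1.1 attach imputation to endpoints, and HAM-A change at Weeks 4 and 8 is the primary and key secondary endpoint, so imputation could be said to carry over. The addendum subscales were never primary, so their rule is weak evidence. Protocol 10.2.2.4 calls these secondary analyses descriptive. This stands as a caution: the reading remains an inference. It does not remove the problem, because under either reading 6.3.1 fails to say how its p-values are computed.

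Per-dose inference under the primary estimand already exists in Step 2, with CIs, and 6.3.1 claims no multiplicity control. That limits the stakes. But Step 2 differences are smoothed through fitted dose-response models and do not replace a direct comparison of one dose with placebo.

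The magnitude rests on assumed rates. The bias is zero when dropout matches and about 0.1 SE at 10%/5%; it reaches 0.3 to 0.4 SE only with a threefold imbalance. At modest rates, disagreement about 0.05 is mostly imputation noise, as 15%/15% shows. Any early-withdrawal or unscheduled HAM-A on Days 22 to 43 counts as Week 4 (SAP 4.3), which reduces losses. The PPS repeat removes subjects with impacting deviations, though it does not restore dropouts. If dropout depends on the unseen score, the remedy leaves more than half the bias. The p-value figures cover only the mechanism that favours imputation. All of this stands and keeps the point at moderate weight.

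**Conclusion.** The point holds. SAP 6.3.1 yields the only per-dose p-values for HAM-A Total Score and states no rule for missing or post-event scores. On the best reading, its Week 4 and Week 8 results handle both differently from the primary and key secondary analyses.

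Under the assumed inputs with Week 2-driven dropout, the bias runs from none (equal dropout) through about 0.2 points (10%/5%) to 0.7-0.9 points (30%/10%), in either direction. Imputation removes it if dropout depends on observed scores, and about 21% to 44% of it if dropout depends on the Week 4 score itself. The difference in post-event handling is one of estimand. The MCP-Mod test, its power and the Step 2 estimates are not affected. This is worth correcting because the remedy is cheap, not because it threatens the primary conclusion.

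**What to change.** In SAP 6.3.1, define the Week 4 and Week 8 dose-placebo differences, CIs and p-values as contrasts of the pooled Step 1 LS means and covariance matrix, using the same 20 imputations, the 6.1.1 intercurrent-event rules and Rubin's rules. Exempt these comparisons from the no-imputation sentence in 4.5. Keep the observed-case ANCOVA as a labelled sensitivity analysis and say that it retains post-event scores. Extending imputation to Weeks 1, 2 and End of Study is optional; otherwise label those visits observed-case.

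The cost is SAP wording and a little programming, because the pooled means and covariance for Weeks 4 and 8 are already produced. The downside is that these supportive tables then depend on the imputation model. The existing addendum followed unblinded review of the primary endpoint, so a change made at or after that stage must be labelled post hoc.
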